By including a wider spectrum of patients with the target condition, the generalizability of the study findings will be greatly enhanced. Unpublished data from a sample of almost 70,000 members of Kaiser Permanente Southern California (KPSC) with incidentally detected pulmonary nodules indicate that nodules ≤ 10 mm make up 53% of the total population of patients with pulmonary nodules; by increasing the size threshold to ≤ 15 mm, we will include an additional 16% of the total nodule population. Even if as many as one third of the study patients with nodules measuring between 11 mm and 15 mm are not managed initially by CT

surveillance, and instead undergo an initial invasive biopsy or surgical procedure, this would still increase the size of the target population considerably and improve generalizability.

By increasing the size of the target population, we will also improve feasibility, both by casting a wider net that helps us to meet enrollment targets more efficiently, and by increasing the expected prevalence of cancer in the enrolled sample. Based on KPSC data, we estimate that 2% of patients with nodules measuring ≤ 10 mm will have a cancerous nodule, whereas 3% of patients with nodules measuring ≤ 15 mm will have a cancerous nodule (including almost 7% of patients with nodules measuring between 11 mm and 15 mm). Because the study is powered to demonstrate equivalence in stage distribution for patients with cancerous nodules, the increase in the expected frequency of cancer will enable us to meet our goals for sample size much more efficiently. Specifically, we anticipate that approximately 1,056 enrolled patients will have a cancerous nodule, which is greater than our initial estimate of approximately 900 patients. Of note, the original required sample size to achieve statistical power of 90% will not change, and the study will have slightly greater power than originally anticipated to demonstrate equivalence between the two comparison arms.

Finally, the proposed change will not introduce bias and therefore does not threaten validity, because both the more frequent and less frequent surveillance groups will include patients with nodules measuring ≤ 15 mm.

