Random assignment to one of the two intervention groups at the hospital or health system level will be performed using matching^{45,46} and re-randomization⁴⁷ to ensure balance among several potential confounders: the volume of CT imaging performed, the setting type (integrated healthcare system vs. academic), KPSC vs. other institutions; racial and ethnic distribution; percentage of patients who are current, former, vs. never smokers; inclusion of patients with screening-detected nodules; frequency in using PET for patients with nodules 11-15mm; timing of notification letters to participants; and distribution of insurance type. A biostatistician at the Data Coordinating Center will generate the allocation scheme using statistical software developed in R by [name] at Vanderbilt^{45,46}. All participating organizations have agreed to accept random assignment to one of the two groups. While many of the participating

institutions operate more than one hospital, all but one will undergo randomization at the health system level, because their information systems for managing radiology results are centralized, so assigning individual hospitals to different groups would be difficult. The one exception is KPSC, which operates hospitals in 11 distinct medical service areas (MSA); clinical and administrative leaders at this site have agreed to randomization at the level of the MSA. Site PIs, clinical champions, and their multidisciplinary collaborators (including radiologists, primary care physicians, pulmonologists, oncologists and surgeons) will work with key administrative leaders and other clinicians to implement the assigned imaging protocols during the study period. Although randomization is at the hospital level, the unit of analysis will be the individual patient, and we will compare patients randomized to more vs. less frequent surveillance, after adjusting for potential clustering within sites.

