To examine whether among participants with cancerous nodules, less intensive surveillance will be non-inferior to more intensive surveillance for the frequency of cancer progression beyond AJCC 7th edition stage T1a (or T1b for 8th edition) disease, we will use hierarchical logistic regression that includes random site effects to account for clustering of patients within sites and to capture institutional characteristics that are not explicitly modeled. Hierarchical logistic regression models will be fitted with and without adjusting for potential confounders including age, gender, ethnicity/race, smoking, body mass index (BMI), baseline nodule size, and any facility-level factors balanced during the randomization.

We will conduct a main analysis and several sensitivity analyses.

1. The main intent to treat analysis will include all enrolled participants in both study arms
2. A modified intent to treat sensitivity analysis will include:
 - a. For integrated healthcare systems, all active members
 - b. For other systems, patients who have at least one follow-up visit
3. On treatment sensitivity analyses will include those who met the definition of adherence to first recommended test and to overall surveillance protocol
4. We will conduct another sensitivity analysis using all nodules, instead of cancerous nodules, as the denominator to evaluate rates instead of proportions, given some concern about the potential for overdiagnosis in the more intensive arm. However, we are concerned about evaluating rates among all nodules due to the potential for differential enrollment of very small, likely insignificant nodules across sites. Inclusion of these nodules in overall rates will inflate the denominator without an increase in

numerator, resulting in smaller rates. Thus, we will evaluate variation in lung cancer rates across site within arms. Significant heterogeneity among the sites will provide evidence that the rates may be unreliable due to differential enrollment.

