5. We will perform additional sensitivity analyses to test the robustness of findings to the source of data. The primary analysis will include data from all three sources (local and state tumor registries and electronic health records). The first sensitivity analysis will be limited to lung cancer outcomes from both state and local tumor registries, truncating follow-up time as necessary to ensure non-differential follow-up across sites (likely at a minimum of 17-18 months). Another sensitivity analysis will be limited to lung cancer outcomes from only state registries, truncating follow-up as per above.
6. A separate analysis will examine patients who adhere to the recommendations for evaluation compared to those who do not, within each of the two study arms and for both arms combined, for the primary outcome of tumor (T) stage >AJCC 7th edition stage T1A (or AJCC 8th edition stage T1b).

H1a - Secondary endpoint:

TNM stage: We will conduct a secondary analysis to compare the presence of AJCC-7 TNM stage >T1aN0M0 or AJCC-8 TNM stage >T1bN0M0 between study arms. This is a secondary analysis because it is not possible to ascertain TNM stage at the time of nodule identification, so we will not be able to compare rates of progression for this outcome. Nevertheless, we will be able to make an unbiased comparison of the presence of TNM stage >T1aN0M0 at the time of diagnosis. Because it is possible that a small percentage of enrolled patients will have minimal or occult N1-3 and/or M1 disease at the time of enrollment, the baseline risk using this outcome definition will be greater than what we assumed for the primary outcome of tumor (T) stage >T1a, and therefore we will have less power to show non-inferiority in this sensitivity analysis.

H1b - Secondary endpoints:

Timeliness of diagnosis: To investigate whether among participants with cancerous nodules, less intensive surveillance will be non-inferior to more intensive surveillance for timeliness of diagnosis, we will restrict our analysis to participants with cancerous nodules and use Cox regression models where time from initial nodule identification to diagnosis is the outcome variable.

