We will continue recruitment through the end of the study to collect additional data for HTE analyses with greater statistical power for Aim 1. We assume 10% loss to follow-up before final diagnosis is established based on KPSC membership data. This yields an estimated sample size for analyses of 960 individuals with cancerous nodules for Aim 1, and 32,000 individuals with small nodules for Aims 2-4.

Aim 1: For the primary outcome, the baseline risk of progression has not been reported. Conservatively, we assume that 5% of patients will progress from a tumor ≤ 15 mm to a tumor > 20 mm during the surveillance period. Assuming a two-sided alpha of 0.05, and an intraclass correlation coefficient (ICC) of 0.01, a sample size of 888 unique patients with cancerous lung nodules (444 per arm) is required to achieve 83% power to detect an absolute increase in tumor progression of 5 percentage points. Thus, our anticipated sample size of 960 unique patients with cancerous lung nodules provides adequate power to show non-inferiority of the less intensive surveillance strategy for our primary outcome of lung cancer stage $> T1a$ at diagnosis. The most uncertainty in our assumptions is for the ICC. We will have at least 80% power to detect a 5% increase in our primary outcome for ICC values of 0.012 or less. At the baseline ICC value of 0.01, a total sample size of 32,560 enrolled (including 888 patients with cancerous nodules) will have 0.83 power; for an ICC value of 0.012, a total sample size of 35,200 enrolled (960 patients with cancer) will also have 0.83 power.

Aim 2: Prior studies of anxiety and distress in lung cancer screening have shown that the identification of a lung nodule leads to anxiety and emotional distress that subsequently dissipates over 1-2 years.^{56 63 52} For our analyses of anxiety and emotional distress, we will have $> 90\%$ power to detect an effect size of 0.22 standard deviation, assuming an ICC of 0.01, even if the response rate is as low as 5%, resulting in an estimated sample size of approximately 792 respondents in each arm.

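### The main Cox models for time to diagnosis, time to treatment and survival name no adjustment covariates, so a real difference in time to diagnosis would be tested with less power than the collected data allow

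*Combined protocol and SAP*

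**What the plan says.** In the Analysis Plan under H1b, the analysis of time to diagnosis is restricted to participants whose nodule proves cancerous and will "use Cox regression models where time from initial nodule identification to diagnosis is the outcome variable". Time to treatment (H1b) and overall survival (H1c) get Cox models of the same form. The text fixes the analysis set, time origin, censoring, a site-clustered sandwich variance and a check of proportional hazards. It names no adjustment covariate. Age, nodule size, attenuation and mode of detection appear only as treatment interactions, in analyses the plan calls exploratory.

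Other models are treated differently. The H1a logistic model is fitted with and without age, gender, ethnicity/race, smoking, BMI, "baseline nodule size, and any facility-level factors balanced during the randomization". Much the same list is given for the H2b, H3a and H4 models.

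Two other places bear on the point. The factors balanced in Cluster Randomization include smoking mix and "frequency in using PET for patients with nodules 11-15mm". Under Inclusion Criteria, the plan expects cancer in 2% of patients with nodules up to 10 mm and 3% of those with nodules up to 15 mm, "including almost 7% of patients with nodules measuring between 11 mm and 15 mm".

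The direction of H1b is not consistent. The Hypotheses section states superiority of more intensive surveillance, the H1b analysis paragraphs state non-inferiority, and the closing time-to-event paragraph returns to superiority. No hazard-ratio margin is given.

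**The concern.** Baseline nodule size is built into the timing of diagnosis. In Tables 2, 3 and C1-C3 it determines when the first repeat CT falls due and whether PET or tissue sampling is an option at once. The Inclusion Criteria acknowledge that some 11-15 mm nodules go directly to PET, biopsy or surgery, and the intention-to-treat population keeps those patients. Size is therefore likely to be among the strongest predictors of time to diagnosis that the trial records.

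In a Cox model, leaving out a strong predictor moves the arm hazard ratio towards 1 relative to the ratio among patients alike on that predictor, even when the arms are balanced. The standard error hardly changes, so a superiority test loses power. H1b in the Hypotheses section expects a real difference, and the Objectives expect only slightly shorter times to diagnosis, so power matters. The silence also leaves the covariate choice open until the data are in hand, although Research Design and Methodology says all analyses will be specified in advance.

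**Working it through.** **1. The plan's own power figure.** None is given for the Cox endpoints. The nearest is for the binary primary outcome: 888 cancers, said to be what "is required to achieve 83% power to detect an absolute increase in tumor progression of 5 percentage points" at ICC 0.01, and "for an ICC value of 0.012, a total sample size of 35,200 enrolled (960 patients with cancer) will also have 0.83 power". Take 24 equal clusters, 5% in both arms, a 5-point margin and one-sided 0.025.

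- 888 cancers: m = 888/24 = 37; design effect = 1 + 36 × 0.01 = 1.36; effective n per arm = 444/1.36 = 326.5. Power = Φ(0.05/√(2 × 0.05 × 0.95/326.5) − 1.96) = Φ(0.97) = 0.834.
- 960 cancers, ICC 0.012: m = 40; design effect = 1 + 39 × 0.012 = 1.468; effective n per arm = 480/1.468 = 327.0; power 0.835.

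The figure reproduces, but it says nothing about the Cox models.

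**2. Share of cancers in the larger nodules.** From the Inclusion Criteria, nodules up to 10 mm are 53% of all nodules with 2% cancer, and 11-15 mm nodules are a further 16% with almost 7% cancer (taken as 7%). Share = 16 × 7/(53 × 2 + 16 × 7) = 112/218 = 51%. As a check, 218/69 = 3.2%, close to the plan's 3%. The cancer set splits about evenly on size, which is where an omitted two-level factor matters most.

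**3. Effect of omitting a prognostic covariate.** All inputs except 960 and 24 are assumptions, because the plan gives no hazard ratio, event count or prognostic strength. Simulated Cox models, 1:1, no clustering, true conditional hazard ratio 1.25 (more versus less intensive), one normal covariate, two-sided 0.05. Everyone in the set is diagnosed, so events = 960. The 700-event column allows roughly for clustering: 960/(1 + 39 × 0.01) = 691. For scale, two equal groups with hazard ratio h have a log-hazard SD of ln(h)/2, so h = exp(2 × SD).

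| Covariate SD | h | Mean HR, unadjusted / adjusted (960) | Power, 960 events | Power, 700 events |
|---|---|---|---|---|
| 0.25 (weak) | 1.65 | 1.23 / 1.24 | 91% / 93% | 80% / 83% |
| 0.5 (moderate) | 2.7 | 1.20 / 1.25 | 80% / 93% | 69% / 87% |
| 1.0 (strong) | 7.4 | 1.15 / 1.25 | 60% / 93% | 48% / 83% |

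The losses at 960 events are about 2, 13 and 33 points. With 600 runs, the Monte Carlo error of one power near 80% is √(0.8 × 0.2/600) = 1.6 points.

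Cross-check with Schoenfeld's formula, power = Φ(ln HR × √960/2 − 1.96): HR 1.25 gives Φ(1.50) = 0.933, HR 1.20 gives Φ(0.86) = 0.806 and HR 1.15 gives Φ(0.21) = 0.581. These agree with the table, so the loss comes from the shrunken hazard ratio.

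With a conditional hazard ratio of 1.20 and 960 events, power is 64% against 80% (SD 0.5) and 42% against 76% (SD 1.0).

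**4. Where the effect is small or absent.**

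- Survival-like case with about 240 to 290 deaths, hazard ratio 1.25: power 39% against 39% (SD 0.25) and 39% against 51% (SD 1.0). The hazard ratio shifts by at most about 0.04.
- Non-inferiority at a true hazard ratio of 1, 960 events, assumed margin 0.80: power 92% to 93% with or without the covariate.

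**The case against.** **The plan may already cover this.** The Abstract promises adjustment for residual imbalances, and the Aim 3 text applies covariates to the regression models mentioned above it. But the Abstract speaks of hierarchical models and names no covariate, and the Aim 3 sentence sits in the H3a paragraph. Neither clearly reaches the Cox models. Even if the second did, fitting with and without covariates would not say which model is the main one.

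**An unadjusted hazard ratio is valid.** This stands. It estimates a marginal effect, and the attenuation is relative to a conditional ratio that the plan does not name as its target. The loss of power in a superiority test remains.

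**The size is assumed.** This also stands. A weak covariate costs only about 2 points.

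Three stronger readings are tempting, and the documents do not support them.

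- A reader might infer that omission makes a false non-inferiority conclusion likelier. That needs a hazard-ratio margin set on the covariate-adjusted scale, and the plan gives no margin on any scale. The missing margin and the unclear direction of H1b are separate matters.
- A reader might infer from the H1a text on uneven enrolment of very small nodules that size mix differs by site in the Cox set, which would enlarge the loss. That text concerns the all-nodules denominator. It says those nodules add nothing to the numerator, so it is no evidence about patients with cancer.
- A reader might infer that all three endpoints lose power alike. The Aim 1 outcomes text expects limited time for deaths to accrue, and step 4 shows the effect on survival may then be negligible.

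**Conclusion.** The point holds in a limited form. The main Cox models name no adjustment covariates, although the variables are collected and used in the plan's other models. For time to diagnosis, analysed as the superiority question in H1b, this gives up power whenever the arms truly differ: about 2, 13 or 33 points for a weak, moderate or strong covariate. Those figures rest on an assumed conditional hazard ratio of 1.25, 960 events and no clustering, and they cannot be derived from the plan. That nodule size lies above the weak end is a judgement from the schedules and the 51% share, not a documented figure. Time to treatment should behave similarly where most patients are treated. For survival the effect may be negligible, and for non-inferiority at a true hazard ratio of 1 there is no loss of power. These are secondary endpoints, and the primary analysis is not affected.

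**What to change.** In the H1b and H1c analysis paragraphs, state that the Cox models are fitted with and without the patient-level covariates listed for H1a: age, gender, race/ethnicity, smoking, BMI and baseline nodule size, the last as a continuous variable. Make the adjusted model the main analysis for time to diagnosis and time to treatment, keep the site-clustered variance, and report the unadjusted model as supportive. For survival, fit both and say in advance which is the main one. Keep facility-level terms few, because 24 clusters leave little between-site information.

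The cost is one sentence. All the variables are already collected, and the plan already provides multiple imputation for missing covariates. The small downside is that the hazard ratio becomes conditional on the covariates and should be described that way. If arm comparisons of these endpoints have already been seen, the adjusted models should be labelled as added later.

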H1a: Among participants with nodules that prove to be cancerous, less intensive surveillance will be non-inferior to more intensive surveillance for: (a) the frequency of cancer progression beyond AJCC 7th edition stage T1a disease (or T1b for AJCC 8th edition) and (b) the frequency of cancer progression beyond AJCC 7th edition TNM stage T1aN0M0 (or T1bN0M0 for AJCC 8th edition). In addition, among participants with *lung nodules*, less intensive surveillance will be non-inferior to more intensive surveillance for: (a) the frequency of cancer progression beyond AJCC 7th edition stage T1a disease (or T1b for AJCC 8th edition); and (b) the frequency of cancer progression beyond AJCC 7th edition TNM stage T1aN0M0 (or T1bN0M0 for AJCC 8th edition).. Furthermore, in exploratory analyses for HTE, we hypothesize that individuals who are most likely to benefit from more intensive surveillance will include older people, people with larger nodules (>8 mm), patients with solid or part-solid nodules (compared with non-solid

nodules), and individuals with nodules detected by screening (compared with individuals who have nodules that are incidentally detected).

H1b: Among participants with nodules that prove to be cancerous, more intensive surveillance will result in more timely diagnosis than less intensive surveillance.

H1c: Among participants with nodules that prove to be cancerous, less intensive surveillance will be non-inferior to more intensive surveillance for overall survival. Among participants with lung nodules, less intensive surveillance will be non-inferior to more intensive surveillance for overall survival.

H2a: Among all participants with a lung nodule ≤ 15 mm, more intensive surveillance will be associated with greater levels of emotional distress and state anxiety at 13-24 months, but levels of distress and anxiety similar to less intensive surveillance at 1-2 months and ≥ 25 months.

H2b: Among all participants with a lung nodule ≤ 15 mm, more intensive surveillance will be associated with scores similar to less intensive surveillance for general health status at 1-2 months, 13-24 months and ≥ 25 months.

H2c: Among participating radiologists and pulmonologists, satisfaction with the surveillance protocol will be greater among those who practice at institutions assigned to the less intensive protocol.

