H3a: Among all participants with a lung nodule ≤ 15 mm, more intensive surveillance will be associated with greater nodule-related resource utilization, including more frequent use of CT scanning, PET scanning and invasive biopsy.

H3b: Among all participants with a lung nodule ≤ 15 mm, more intensive surveillance will be associated with a greater number of serious complications related to invasive procedures, including pneumothorax, pneumothorax requiring tube thoracostomy, bleeding, acute respiratory failure, acute renal failure and acute myocardial infarction.

H3c: Among all participants with a lung nodule ≤ 15 mm, more intensive surveillance will be associated with greater total exposure to diagnostic radiation than less intensive surveillance.

H4: Among all participants with a lung nodule ≤ 15 mm, more intensive surveillance will be associated with worse adherence to the surveillance protocol than less intensive surveillance, when measured at the level of the interpreting radiologist, the ordering provider and the patient.

Analysis Plan

In most cases, the unit of analysis will be the individual patient. All primary analyses will be by intention to treat, although we will also perform sensitivity analyses by surveillance imaging actually received. The intention to treat population will include all patients with qualifying nodules, even ones who do not undergo surveillance as the initial step in their evaluation (i.e., patients that proceed directly to tissue diagnosis). Sensitivity analyses will evaluate outcomes by strategy recommended and by surveillance imaging received.

Descriptive statistics will be generated for continuous variables (e.g., mean, standard deviation, median, range) and categorical variables (frequency) at baseline and follow-ups when appropriate. Bivariate analyses will include comparisons of means or medians (as appropriate) for continuously measured variables, cross tabulations of categorical variables, and Kaplan-Meier plots for time to event outcomes. Count outcomes, such as the number of procedure-related complications, will be treated as Poisson random variables. Analysis of time to

diagnosis, treatment, and survival will use Cox regression, after checking the proportionality assumption by creating log-minus-log plots.

H1a - Primary endpoint –lung cancer stage >T1a at diagnosis:

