Timeliness of treatment: To investigate whether among participants with cancerous nodules, less intensive surveillance will be non-inferior to more intensive surveillance for timeliness of treatment, we will restrict our analysis to participants with cancerous nodules and use Cox regression models where time from initial nodule identification to treatment is the outcome variable. Patients who die or do not receive treatment will be censored at end of follow-up. We will consider using competing risk models, as necessary.

H1c: Secondary endpoint

Survival: To investigate whether among participants with cancerous nodules, less intensive surveillance will be non-inferior to more intensive surveillance for overall survival, we will restrict our analysis to participants with cancerous nodules and use Cox regression models where time from initial nodule identification to death as the outcome variable. Patients will be censored at end of follow-up.

For all time-to-event analyses, clustering by site will be handled by specifying subjects nested within each cluster and using robust sandwich estimators for statistical inferences.⁶¹ The proportionality assumption will be checked by creating log-minus-log plots. To explore whether individuals who are most likely to benefit from more intensive surveillance, subgroup analyses will examine the effect of age (using the median and/or quartile values as cut points), nodule size (>8 mm), nodule attenuation (solid or part-solid nodules compared with non-solid nodules), and mode of detection (detected by screening compared with incidentally detected).

Analytically, we will include interaction terms between each of these factors with treatment in the models, respectively. For significant interactions, we will also conduct subgroup analysis to explore the treatment effects in corresponding subgroups. Since the study is not powered to test interaction terms, these analyses will be exploratory. For H1b, to study whether among participants with cancerous nodules, more intensive surveillance will result in more timely diagnosis and treatment than less intensive surveillance, we will adopt similar strategy used for comparing overall survival described above.

H2a:

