Appendix C: Surveillance Protocols

Table C1: Surveillance protocol for incidental nodules, Group A, more intensive surveillance

Patient and Nodule characteristics		Surveillance times (months from index CT)
Solid, with Risk Factors		
≤4		12
>4 to ≤6		6, 18
>6 to ≤8		3, 9, 21 to 24
>8		3, 9, 21 to 24 or PET or tissue
Solid, without Risk Factors		
≤4		Optional (12)
>4 to ≤5		12
>5 to ≤8		6, 18
>8		3, 9, 21 to 24 or PET or tissue
Part-solid		
Solitary, solid component ≤5		3, 15, 27, 39
Solitary, solid component >5		3, tissue if persists
Multiple, solid component ≤5		3, 15, 27, 39
Multiple, solid component >5		3, tissue if persists and solid ≥5
Non-solid		
≤5, solitary		None
>5, solitary		3, 15, 27, 39
≤5, multiple		24, 48
>5, multiple		3, 15, 27, 39

Table C2: Surveillance protocol for incidental nodules, Group B, Less intensive surveillance

Nodule characteristics	Surveillance times (months from index CT)
Solid	
<6, solitary or multiple	None (Optional at 12 months in patients with risk factors)
≥6 to ≤8, solitary	12, 24
≥6 to ≤8, multiple	6, 18
>8, solitary or multiple	3, 15, 27 or PET or tissue
Part-solid	
<6, solitary	None
<6, multiple	6, 24, 48
≥6, solid component <6	6, 18, 30, 42, 54, 66
≥6, solid component ≥6	6, tissue if persists
Non-solid	
<6, solitary	None
≥6, solitary	12, 36, 60
<6, multiple	6, 24, 48
≥6, multiple	6, 24, 48

Table C3: Surveillance protocols for screening-detected nodules

Lung-RADS Category	Nodule characteristics	Surveillance times (months from index CT)		
		Group A	Group B	
1	No nodule	12, 24...	12, 24...	
	Calcified nodule			
	Fat-containing nodule			
2	Solid nodule <4	12, 24...	12, 24...	
	Solid nodule <6	6, 18, 30...		
	New solid nodule <4			
	Part-solid nodule <6			
	Non-solid nodule <20			
	Non-solid nodule ≥20, unchanged or slow-growing			
	Category 3 or 4 nodule unchanged for >3 months			
3	Solid nodule ≥6 to <8	3, 15, 27...	6, 18, 30...	
	New solid nodule, ≥4 to <6			
	Part-solid nodule ≥6, with solid component <6			
	Part-solid nodule, new <6			
	Non-solid nodule ≥20			
4A	Solid nodule ≥8 to <15	3, 9, 21... (PET may be used when solid component ≥8)	3, 15, 27... (PET may be used when solid component ≥8)	
	Solid nodule, new ≥6 to <8, or growing <8			
	Part-solid nodule ≥6, with solid component ≥6 to <8			
	Part-solid nodule, new or growing, with solid component <4			
	Endobronchial nodule			
4B	Solid nodule ≥15	CT at 3 months, PET or tissue, depending on probability of cancer and comorbidities		

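### Time to diagnosis and time to treatment each rest on one Cox hazard ratio, although the staggered scan schedules make crossing hazards foreseeable and nothing follows if the proportionality check fails

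*Combined protocol and SAP*

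**What the plan says.** The H1b secondary-endpoint section of the Analysis Plan restricts both timeliness analyses to cancer cases. For diagnosis it will "use Cox regression models where time from initial nodule identification to diagnosis is the outcome variable"; for treatment it will "use Cox regression models where time from initial nodule identification to treatment is the outcome variable". Clustering by site is handled with robust sandwich errors.

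Proportional hazards are addressed twice. The opening of the Analysis Plan says that analysis of time to "diagnosis, treatment, and survival will use Cox regression, after checking the proportionality assumption by creating log-minus-log plots", and the time-to-event paragraph after H1c repeats that "The proportionality assumption will be checked by creating log-minus-log plots". Neither place says what happens if the plots show non-proportionality. The plan also has "Kaplan-Meier plots for time to event outcomes" as description and, for treatment, "We will consider using competing risk models, as necessary". The latter concerns competing events, not hazards that change over time.

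The direction of H1b differs by place. The Hypotheses section says "more intensive surveillance will result in more timely diagnosis than less intensive surveillance", and the end of the time-to-event paragraph repeats that direction for diagnosis and treatment. The two timeliness paragraphs instead describe non-inferiority of the less intensive arm and give no margin.

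The sample size section gives follow-up of at least 2 years. A 26-month window is defined for Aim 3 resource use. No horizon is given for H1b.

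Appendix C sets the scan months. In Table C2 the solid row "≥6 to ≤8, solitary" has 12 and 24 months.

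**The concern.** Cancers under surveillance are found largely at scans, and the arms are defined by scan timing. Group A has extra scans in the first year. Group B's scans at 12 and 15 months then find cancers that Group A has already removed from its risk set. Group A's diagnosis hazard should therefore be higher early and Group B's higher later. A single hazard ratio averages the two, with weights that depend on when follow-up stops.

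H1b is where the trial measures what less scanning costs in delay. If the average sits near 1, the superiority wording leads to a report of no difference although diagnosis was delayed. Under the non-inferiority wording, the same pull towards 1 makes the conclusion too easy to reach.

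**Working it through.** **1. The plan's own figure.** No power, hazard ratio or margin is given for H1b. The only Aim 1 power figure is 83% for the binary primary outcome, and it reproduces:
- cluster size 888/24 = 37; design effect 1 + 36 × 0.01 = 1.36; effective n per arm 444/1.36 = 326.5;
- standard error √(2 × 0.05 × 0.95/326.5) = 0.01706;
- z = 0.05/0.01706 − 1.96 = 0.97, so power is 0.83.

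For 960 cancers the cluster size is 40 and the design effect is 1 + 39 × 0.01 = 1.39.

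**2. The schedules (Tables C1 and C2, incidental nodules, months from index CT).**

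| Solid nodule | Group A | Group B |
|---|---|---|
| >6 to ≤8 mm (A: with risk factors; B: solitary, from 6 mm) | 3, 9, 21 to 24 | 12, 24 |
| >8 mm | 3, 9, 21 to 24 | 3, 15, 27 |

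For >8 mm the first scan coincides. Group A alone scans at month 9 and Group B alone at month 15. For 6–8 mm, Group A has two scans before Group B's first. Table 2 gives month 24 where Table C1 gives 21 to 24.

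**3. Hazards by interval (simulated).** There were 960/2 = 480 cancers per arm. The following are assumptions, not document figures: 30–75% of cancers >8 mm, 15–33% of those worked up at once, 50–90% of scans attended, detection rising with time since index CT, mean work-up lag 1.5 months, scan timing SD 1 month, diagnosed cancers only. With mixed sizes and a 26-month window, the A/B hazard ratio by 3-month interval from 0 to 24 months was 0.89, 1.18, 1.42, 5.35, 0.98, 0.38, 0.42, 0.62. It crossed 1 in every setting for which intervals were tabulated. By month 12, 75% (A) and 57% (B) were diagnosed. The ratio of cumulative hazards to month 12 is ln(0.25)/ln(0.43) = 1.386/0.844 = 1.64, yet the Cox hazard ratio was only 1.03–1.06.

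**4. Effect of the cut-off alone.** One setting (75% of cancers >8 mm, 33% worked up at once, 70% of scans attended), with only the window changed:

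| Window (months) | Diagnosed by month 12, A vs B | Cumulative-hazard ratio to month 12 | Cox hazard ratio |
|---|---|---|---|
| 24 | 80% vs 60% | ln 0.20/ln 0.40 = 1.76 | 1.15 |
| 26 | 72% vs 59% | ln 0.28/ln 0.41 = 1.43 | 0.91 |
| 36 | 65% vs 49% | ln 0.35/ln 0.51 = 1.56 | 1.22 |

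A cut-off between Group A's last scan and Group B's month-27 scan counts Group A's late diagnoses and omits Group B's.

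**5. A second set of assumptions.** The share of cancers at 11–15 mm was derived from the Inclusion Criteria text: 16% of nodules at about 7% cancer against 53% at 2% gives 1.12/(1.12 + 1.06) = 51%. The rest was assumed: 15% >8–10 mm, 20% 6–8 mm, 14% <6 mm. Across cut-offs, growth models and placement of Group A's 21-to-24-month scan, the Cox hazard ratio ran from 0.66 to 1.42, while Group A always led at month 12. In one case 73% against 50% were diagnosed by month 12, a cumulative-hazard ratio of ln(0.27)/ln(0.50) = 1.309/0.693 = 1.89. The Cox hazard ratio there was 0.92.

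**6. Power (illustrative, unclustered, 60% of cancers >8 mm).**

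| Window (months) | Cox | Restricted mean time to 18 months |
|---|---|---|
| 24 | 0.47–0.98 | 0.83–0.98 |
| 26 | 0.00–0.83 | 0.24–0.95 |
| 36 | 0.89–0.99 | 0.68–0.99 |

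If all cancers are 6–8 mm, both methods have about 0.95–1.00. Time to treatment was not simulated. It has the same structure, plus censoring of untreated patients.

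**The case against.** The strongest reply is that the plan does not ignore the assumption. It checks it, draws Kaplan-Meier curves that show timing by arm, and includes an exploratory interaction with nodule size. H1b is secondary and carries no power claim. All this is right, so the gap is a check without a consequence, not an unexamined assumption.

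A reader might infer that the effects must cancel and that power is certainly lost. The documents do not support that. They give no size mix of cancers, detection probability or expected hazard ratio, and Cox loses nothing material in several settings in step 6. Adherence is imperfect (the plan assumes 27% non-adherence in the more intensive arm), and some rows coincide: Group A solid >5 to ≤8 mm without risk factors and Group B multiple 6–8 mm are both at 6 and 18 months. This dilutes the stagger, although the hazards still crossed with 50–90% attendance.

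A reader might also infer that restricted mean time to 24 months should simply replace Cox. It is not uniformly better. With undiagnosed cancers censored at 24 months and Group A's third scan at month 21, power was 58% for Cox against 35% (exponential growth time, mean 9 months), 88% against 6% (uniform) and 79% against 76% (mean 6). Among diagnosed cancers, with uniform growth and that scan at month 21, it favoured the wrong arm.

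One objection also applies to the remedy below: any analysis of diagnosed cases inherits the selection made by the cut-off. This is why the horizon must be fixed first. Month 12 is itself a Group B scan month, so the contrast there shows the delay near its largest. Month 18 is needed beside it.

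**Conclusion.** The concern holds as a foreseeable failure of proportional hazards that the plan checks but does not act on, combined with an unfixed horizon. That the schedules are staggered, that the check has no consequence and that H1b has two directions can all be read directly from the documents. That the averaged hazard ratio can reach or pass 1 while Group A diagnoses more cancers by month 12 rests on simulation under assumed size mix, growth, attendance and work-up lag. The direction of the month-12 contrast was stable across those assumptions; the hazard ratio was not (0.66 to 1.42). The size of any power loss cannot be fixed from the documents, and the powers above are illustrations only. The primary outcome is unaffected. The change is worth making because H1b is the trial's direct measure of delay.

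**What to change.** In the H1b secondary-endpoint section and the time-to-event paragraph that follows H1c:

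1. State one common follow-up horizon for H1b that does not fall among the late scans of either arm (Group A 21 to 24; Group B 24 and 27 months), allowing for work-up time. A horizon before month 21 lies within everyone's follow-up; one after month 27 needs more than the 2-year minimum. No month clears every row of Appendix C, so state the choice and the reason. State also how Table 2's month 24 and Table C1's 21 to 24 are to be read together.
2. Make the between-arm difference in the proportion diagnosed, and in the proportion treated, by fixed months including 12 and 18 the main H1b summary, with site clustering kept.
3. Report the restricted mean time difference to the stated horizon as supportive.
4. Show Cox hazard ratios separately before and after month 12, not as one average. This also gives the log-minus-log check a consequence.
5. Reconcile the superiority and non-inferiority wording of H1b; if non-inferiority is kept, state a margin on the chosen scale.

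The cost is SAP wording and standard software, with no new data. The downside is that several fixed-time contrasts replace one hazard ratio, so the months must be named in advance.
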